### **Adverse Drug Reactions for Ethambutol**

**Common (>10%):** Appetite loss; disorientation; dizziness; general body discomfort; headache; nausea, stomach upset, vomiting

**Uncommon (<3%):** Severe allergic reactions (rash; hives; itching; difficulty breathing; tightness in the chest; swelling of the mouth, face, lips, or tongue); chest pain or tightness; confusion; dark urine; easy bruising or bleeding; fever, chills, or sore throat; hallucinations; joint pain, swelling, or severe tenderness; lower back pain; numbness or tingling of the hands, legs, or feet; severe stomach pain; swollen glands in the neck or armpit; vision loss or other vision changes; yellowing of the skin or eyes.

**Rare (<1%):** decreases in visual acuity, including irreversible blindness, which appear to be due to optic neuritis. Optic neuropathy including optic neuritis or retrobulbar neuritis occurring in association with ethambutol therapy may be characterized by one or more of the following events: decreased visual acuity, scotoma, color blindness, and/or visual defect. These events have also been reported in the absence of a diagnosis of optic or retrobulbar neuritis. Optic neuropathy has not been reported in participants on therapy <90 days.

### **5.2.3 Azithromycin**

Macrolides inhibit RNA-dependent protein synthesis by reversibly binding to the 50 S ribosomal subunits of susceptible microorganisms. Its pharmacokinetics are as follows: The bioavailability of azithromycin after oral administration is approximately 40%. Administration with food, particularly a high fat meal, increases the maximum concentration, but does not affect the overall absorption of the drug. In a study of adults receiving a standard regimen of 500 mg on day 1 followed by 250 mg on days 2-5, the maximum concentration was 0.24 mcg/ml, with a time to achieve maximum concentration of 3.2 hours and an average area under the concentration curve (AUC) of 2.1 mcg·hr/ml. Azithromycin is widely distributed throughout the body, with a volume of distribution in adults of 31.1 L/kg. Protein binding is concentration dependent, ranging from 7 to 51%. Azithromycin penetrates well into the lungs, tonsils, and middle ear fluid, with concentrations exceeding those in the blood. Although azithromycin has extensive tissue distribution, only minimal concentrations have been measured in cerebrospinal fluid. The primary route of elimination of azithromycin is through biliary excretion, as unchanged drug. Only 6-14% of a dose is excreted unchanged in the urine. Azithromycin has an apparent clearance of 630 ml/min in adults, with a terminal elimination half-life of 68 hours.

### **Adverse Drug Reactions for Azithromycin**

**Common (>10%):** Diarrhea; headache; loose stools; nausea; stomach pain; upset stomach; vomiting.

**Uncommon (<3%):** Severe allergic reactions (rash; hives; itching; difficulty breathing; tightness in the chest; swelling of the mouth, face, lips, or tongue; unusual hoarseness); bloody stools; changes in hearing or hearing loss; chest pain; eye or vision problems; irregular heartbeat; muscle weakness; pounding in the chest; red, swollen, blistered, or peeling skin; ringing in the ears; seizure; severe diarrhea; stomach cramps/pain; trouble speaking or swallowing; yellowing of the skin or eyes, decreased hemoglobin, hematocrit, lymphocytes, neutrophils and blood glucose; elevated serum creatinine phosphokinase, potassium, ALT, GGT, AST, BUN, creatinine, blood glucose, platelet count, lymphocytes, neutrophils and eosinophils;

**Rare (<1%):** leukopenia, neutropenia, decreased sodium, potassium, platelet count, elevated monocytes, basophils, bicarbonate, serum alkaline phosphatase, bilirubin, LDH and phosphate. The majority of participants with elevated serum creatinine also had abnormal values at baseline.

## 5.2.4 Rifamycins (Rifampin or Rifabutin)

### 5.2.4a Rifampin

Rifampin inhibits DNA-dependent RNA polymerase activity in susceptible cells. Specifically, it interacts with bacterial RNA polymerase but does not inhibit the mammalian enzyme. Rifampin is readily absorbed from the gastrointestinal tract. Peak serum concentrations in healthy adults and pediatric populations vary widely from individual to individual. Following a single 600 mg oral dose of rifampin in healthy adults, the peak serum concentration averages 7 mcg/mL but may vary from 4 to 32 mcg/mL. Absorption of rifampin is reduced by about 30% when the drug is ingested with food. Rifampin is widely distributed throughout the body. It is present in effective concentrations in many organs and body fluids, including cerebrospinal fluid. Rifampin is rapidly eliminated in the bile, and an enterohepatic circulation ensues. During this process, rifampin undergoes progressive deacetylation so that nearly all the drug in the bile is in this form in about 6 hours. This metabolite is microbiologically active. Intestinal reabsorption is reduced by deacetylation, and elimination is facilitated. Up to 30% of a dose is excreted in the urine, with about half of this being unchanged drug. Rifampin is about 80% protein bound. Most of the unbound fraction is not ionized and, therefore, diffuses freely into tissues. In healthy adults, the mean biological half-life of rifampin in serum averages  $3.35 \pm 0.66$  hours after a 600 mg oral dose, with increases up to  $5.08 \pm 2.45$  hours reported after a 900 mg dose. With repeated administration, the half-life decreases and reaches average values of approximately 2 to 3 hours. The half-life does not differ in patients with renal failure at doses not exceeding 600 mg daily, and consequently, no dosage adjustment is required. Following a single 900 mg oral dose of rifampin in patients with varying degrees of renal insufficiency, the mean half-life increased from 3.6 hours in healthy adults to 5.0, 7.3, and 11.0 hours in patients with glomerular filtration rates of 30 to 50 mL/min, less than 30 mL/min, and in anuric patients, respectively.

### 5.2.4b Rifabutin

Rifabutin is an antimycobacterial agent. It is a semisynthetic ansamycin antibiotic derived from rifamycin S. Mycobutin capsules for oral administration contain 150 mg of rifabutin per capsule, along with the inactive ingredients microcrystalline cellulose, magnesium stearate, red iron oxide, silica gel, sodium lauryl sulfate, titanium dioxide, and edible white ink. Following a single oral dose of 300 mg to nine healthy adult volunteers, rifabutin was readily absorbed from the gastrointestinal tract with mean ( $\pm$ SD) peak plasma levels ( $C_{max}$ ) of 375 ( $\pm$ 267) ng/ml (range: 141-1033 ng/ml) attained in 3.3 ( $\pm$ 0.9) hours ( $T_{max}$  range: 2-4 hours). Plasma concentrations post- $C_{max}$  declined in an apparent biphasic manner. Kinetic dose-proportionality has been established over the 300-600 mg dose range in nine healthy adult volunteers (crossover design) and in 16 early symptomatic human immunodeficiency virus (HIV)-positive patients over a 300-900 mg dose range. Rifabutin was slowly eliminated from plasma in seven healthy adult volunteers, presumably because of distribution-limited elimination, with a mean terminal half-life of 45 ( $\pm$ 17) hours (range: 16-69 hours). Although the systemic levels of rifabutin following multiple dosing decreased by 38%, its terminal half-life remained unchanged. Rifabutin, due to its high

lipophilicity, demonstrates a high propensity for distribution and intracellular tissue uptake. Estimates of apparent steady-state distribution volume ( $9.3 \pm 1.5$  L/kg) in five HIV-positive patients, following IV dosing, exceed total body water by approximately fifteenfold. Substantially higher intracellular tissue levels than those seen in plasma have been observed in both rat and man. The lung to plasma concentration ratio, obtained at 12 hours, was found to be approximately 6.5 in four surgical patients administered an oral dose. Mean rifabutin steady-state trough levels ( $C_{p,min}$ ; 24-hour post-dose) ranged from 50 to 65 ng/ml in HIV-positive patients and in healthy adult volunteers. About 85% of the drug is bound in a concentration-independent manner to plasma proteins over a concentration range of 0.05-1  $\mu$ g/ml. Binding does not appear to be influenced by renal or hepatic dysfunction.

Because treatment with rifabutin may be associated with neutropenia, and more rarely thrombocytopenia, physicians should consider obtaining hematologic studies periodically in patients receiving rifabutin prophylaxis. Urine, feces, saliva, sputum, perspiration, tears, and skin may be colored brown-orange with rifabutin and some of its metabolites. Soft contact lenses may be permanently stained. Patients to be treated with rifabutin should be made aware of these possibilities.

Because of the structural similarity of rifabutin and rifampin, rifabutin may be expected to have some effect on these drugs as well. However, unlike rifampin, rifabutin appears not to affect the acetylation of isoniazid. When rifabutin was compared with rifampin in a study with 8 healthy normal volunteers, rifabutin appeared to be a less potent enzyme inducer than rifampin.

### **Adverse Drug Reaction for Rifamycins (Rifampin or Rifabutin)**

**Common (>10%):** tired feeling; or red or orange colored urine, stools, tears, sweat, or saliva

**Uncommon (<3%):** Allergic reaction (hives; difficulty breathing; swelling of your face, lips, tongue, or throat), fever, chills, body aches, flu symptoms, joint pain or swelling, easy bruising or bleeding, weakness, urinating less than usual or not at all, nausea, stomach pain, loss of appetite, itching, dark urine, clay-colored stools, jaundice (yellowing of the skin or eyes), neutropenia (a low white blood cell count that may make it more likely for you to get infections).

**Rare (<1%):** Rifampin has been shown to produce liver dysfunction. Fatalities associated with jaundice have occurred in patients with liver disease and in patients taking rifampin with other hepatotoxic agents. Patients with impaired liver function should be given rifampin only in cases of necessity and then with caution and under strict medical supervision. In these patients, careful monitoring of liver function, especially SGPT/ALT and SGOT/AST should be carried out prior to therapy and then every 2 to 4 weeks during therapy. If signs of hepatocellular damage occur, rifampin should be withdrawn. Hematological side effects have included thrombocytopenia, leukopenia, hemolytic anemia, and decreased hemoglobin, in less than 1% of patients. Hyperbilirubinemia and hepatitis have been reported in up to 3% of patients. Approximately 50% of hepatotoxicity has been observed during the first month of therapy.

### **5.3 Study Drug Dosing and Administration:**

The following oral CLEAR medications or matching placebo will be introduced as follows:

Day 0 Start: Azithromycin: 250mg po QD (or 500 3 days/week if toxicity) x 8 weeks *and*  
Ethambutol: 1200 mg po QD for  $\geq 50$ kg; <50kg 800 mg po QD (or 3 days/week if toxicity) x 8 weeks  
Rifampin 600 mg QD or Rifabutin 300mg po QD (or 3 days/week if toxicity) x 16 weeks  
Levaquin: 500 mg po QD (or 3 days/week if toxicity) x 16 weeks

Participants will be allowed to take their regimen three times/week instead of daily (which has been shown to be equally efficacious) if toxicity occurs that is thought to be drug related. In addition, if toxicity warrants, one or more drugs can be discontinued and the participant can continue to participate.

The site PI may also elect to stagger the start of study drugs to help identify which drugs may be eliciting which side effects. The study drugs would be introduced starting with Azithromycin and Ethambutol at the baseline visit (day 0) and introducing Rifampin (or Rifabutin) the following week (day 7), and Levaquin one week later (day 14) using the same dosages as above.

#### **5.4 Interruptions in Study Drug Administration for Toxicity**

Due to the large pill burden of seven capsules a day, participants may have toxicities such as nausea. If nausea persists, it is acceptable for a participant to take up to a one-time five day drug holiday while the nausea improves. If a drug holiday is taken, the drug schedule and subsequent visit schedule should be adjusted such that the full sixteen week course is completed.

An expected side effect of Levaquin is extreme joint pain and the investigator should work closely with their primary care physician to manage participant's pain if possible, so the drug does not have to be discontinued.

##### **5.4.1 Drug Toxicity During 2-drug Phase**

To avoid single drug therapy during the 8 weeks of 2-drug therapy, the following order of replacement drug should be followed:

If rifamycin is stopped due to toxicity:

- 1st - azithromycin + levaquin
- 2nd – ethambutol + levaquin
- 3rd – only levaquin

If Levaquin is stopped due to toxicity:

- 1st - azithromycin + rifamycin
- 2nd – ethambutol + rifamycin
- 3rd – only rifamycin

Single drug therapy should be avoided if at all possible.

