#### 4.5.3 Rationale for exclusions

Patients less than 18 years old are excluded because we are not sure that sarcoidosis is the same syndrome in children. No cited studies to date have been performed in children. Exclusion criteria are related to exacerbation of drug allergy or possibly drug toxicity. Concomitant obstructive lung disease could hinder detection of clinical improvement. Patients who are negative for ESAT-6 immune responses will not be included because Phase I trial demonstrated minimal or no improvement in FVC with the CLEAR regimen. Ethambutol is associated with optic neuropathy including optic neuritis or retrobulbar neuritis occurring in association with Ethambutol therapy may be characterized by one or more of the following events: decreased visual acuity, scotoma, color blindness, and/or visual defect. Optic neuropathy has not been reported in participants on therapy <90 days. Levaquin can prolong the QT interval or induce Torsades de Pointe. Other exclusions are related either to safety or complexity and potential for interfering with assessing a response to CLEAR therapy.

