#### 9.1.2 Ethambutol:

**Common ( $> 10\%$ ):** Appetite loss; disorientation; dizziness; general body discomfort; headache; nausea, stomach upset, vomiting

**Uncommon ( $< 3\%$ ):** Severe allergic reactions (rash; hives; itching; difficulty breathing; tightness in the chest; swelling of the mouth, face, lips, or tongue); chest pain or tightness; confusion; dark urine; easy bruising or bleeding; fever, chills, or sore throat; hallucinations; joint pain, swelling, or severe tenderness; lower back pain; numbness or tingling of the hands, legs, or feet; severe stomach pain; swollen glands in the neck or armpit; vision loss or other vision changes; yellowing of the skin or eyes.

**Rare ( $< 1\%$ ):** decreases in visual acuity, including irreversible blindness, which appear to be due to optic neuritis. Optic neuropathy including optic neuritis or retrobulbar neuritis occurring in association with ethambutol therapy may be characterized by one or more of the following events: decreased visual acuity, scotoma, color blindness, and/or visual defect. These events have also been reported in the absence of a diagnosis of optic or retrobulbar neuritis. Optic neuropathy has not been reported in participants on therapy  $< 90$  days

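### The replacement order in section 5.4.1 can extend ethambutol from the stated 8 weeks to as much as 112 days, and this is not reconciled with the plan's only duration-based eye-safety statement (under 90 days).

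*Combined protocol and SAP*

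**What the plan says.** **Planned duration.** In section 5.3 the ethambutol line ends "800 mg po QD (or 3 days/week if toxicity) x 8 weeks", and azithromycin is also given for 8 weeks. The other two drugs run longer: "Levaquin: 500 mg po QD (or 3 days/week if toxicity) x 16 weeks" and "Rifampin 600 mg QD or Rifabutin 300mg po QD (or 3 days/week if toxicity) x 16 weeks". Weeks 9 to 16 are therefore the two-drug phase.

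**Replacement.** Section 5.4.1 governs toxicity in that phase: "To avoid single drug therapy during the 8 weeks of 2-drug therapy, the following order of replacement drug should be followed". Where the rifamycin is the drug lost, the first choice is azithromycin with Levaquin and the second is "ethambutol + levaquin". If Levaquin is stopped, the order is the same with rifamycin as the partner. Levaquin or rifamycin alone comes third and is to be avoided where possible. The section gives no limit specific to ethambutol and does not refer back to the 8 weeks in 5.3.

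**Overall cap.** The synopsis limits treatment to 112 days. Section 5.6 limits it to 112 doses or 16 weeks after randomization, whichever is first.

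**Eye safety.** Section 4.5.3 states: "Optic neuropathy has not been reported in participants on therapy <90 days". Sections 5.2.2 and 9.1.2 repeat it, directly after listing among rare reactions "decreases in visual acuity, including irreversible blindness, which appear to be due to optic neuritis". Colour vision is screened at entry by personal history (exclusion 17). New signs or symptoms and adverse events are recorded at weeks 4, 8, 16 and 24, but no visit list in section 6 and no row of Appendix A names a visual check.

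**The concern.** An 8-week course lies well inside the period that the eye-safety statement covers. A second course under 5.4.1 may not. A site that follows the replacement order exactly can take an active-arm patient to an ethambutol exposure about which the protocol is silent, for a harm that it describes as possibly irreversible. A reader of 5.3 and the risk sections alone would not know that the longer exposure is permitted.

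The route is foreseeable. Section 5.4 treats severe joint pain as an expected Levaquin effect. Section 5.2.4 says that about half of hepatotoxicity is seen in the first month of therapy. Section 5.3 lets drugs be dropped for toxicity, so a patient can reach week 9 with only one of the two continuing drugs. Section 5.2.3 lists several gastrointestinal effects of azithromycin, the first-choice replacement, as common.

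**Working it through.** **Inputs**

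- Ethambutol course: 8 weeks × 7 = 56 days from day 0 (section 5.3).
- Rifamycin and Levaquin: 16 weeks × 7 = 112 days (section 5.3).
- Two-drug phase: 112 − 56 = 56 days, which agrees with the 8 weeks in section 5.4.1.
- Treatment cap: 112 days (synopsis) or 16 weeks (section 5.6). The phases reproduce it: 56 + 56 = 112.
- Eye-safety statement: under 90 days (sections 4.5.3, 5.2.2, 9.1.2).

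**Assumptions.** The first 56 days of ethambutol are completed, and replacement continues to day 112.

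**Cumulative count.** If ethambutol restarts after day s, with s from 56 to 112, total exposure is 56 + (112 − s).

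| Restart after day | Cumulative ethambutol days |
|---|---|
| 56 | 112 |
| 63 | 105 |
| 70 | 98 |
| 77 | 91 |
| 78 | 90 |
| 79 | 89 |
| 84 | 84 |

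The maximum is 112 days. That is 112 − 56 = 56 days beyond the course in 5.3 and 112 − 90 = 22 days beyond the 90-day mark. Setting 56 + (112 − s) > 90 gives s < 78. A restart after day 78 gives exactly 90 days, which is already not under 90. Later restarts exceed 56 days but stay under 90.

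**Continuous count.** With no gap at day 56, ethambutol runs unbroken for 112 days. With a real gap, the first run is 56 days and the second is 112 − s, which is less than 56, so neither reaches 90. The documents do not say how long a gap must be to break continuity.

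**Modifiers.** Dosing three days a week reduces the number of doses but not the duration, and the safety statement is expressed in days. The staggered start in 5.3 would put the end of a full 16-week Levaquin course at day 14 + 112 = 126. A five-day drug holiday under 5.4 would put the end of treatment at day 112 + 5 = 117. Both sit uneasily with the 16-week cap in 5.6; 112 days is the figure under that cap.

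**The case against.** The strongest defence is that no stated limit is broken. Section 5.3 gives the default course, 5.4.1 is an express toxicity exception, and the protocol nowhere undertakes to keep ethambutol under 90 days. That is a fair reading, and 5.4.1 may well be deliberate. It does not settle the point, because an intended exception still leaves the permitted exposure unstated and the 90-day statement unqualified.

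Four stronger readings are tempting, and the documents do not support them.

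- **Ethambutol reuse is unlimited.** It is not: the 112-day or 16-week cap applies to the whole regimen.
- **Reuse is compulsory.** It is not: azithromycin comes first, and the third option is a single drug, discouraged but allowed.
- **Visual harm would go unrecorded.** Symptoms and adverse events are recorded at weeks 4, 8, 16 and 24, and the medication diary is reviewed for new symptoms (section 5.5). Section 5.1 calls for all four drugs to be stopped for a significant safety issue thought related to study drug, and section 12.1 makes intolerable toxicity a stop point. What is missing is anything directed at vision.
- **Risk is shown to rise between days 90 and 112.** The documents say nothing either way. The risk sections also list loss of vision without tying it to duration, so the 90-day statement is not their only content on eye harm.

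The continuous reading of the 90 days also has force: it leaves only near-immediate restarts beyond the mark. Since the protocol does not say which count it means, that is part of what needs settling.

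**Conclusion.** The point holds as a failure to reconcile. Followed as written, the plan permits up to 112 days of ethambutol against a stated course of 56, while its only duration-based eye-safety statement stops short of 90 days.

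The size depends on the count. Cumulatively, restarts before day 78 pass 90 days, under the assumptions of a completed first course and replacement to day 112. Continuously, only a restart with almost no gap does so.

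The affected group is narrow. A patient must be in the active arm, lose rifamycin or Levaquin, not be given azithromycin as the replacement, and restart early enough. The documents give no basis for estimating how many patients that is. The primary analysis is not called into question. The point deserves correction because the potential harm is serious and the correction is cheap, but it does not show that the trial is unsafe or that the replacement order is wrong.

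**What to change.** Reconcile section 5.4.1 with the 8-week course in 5.3 and with the 90-day statement in 4.5.3, 5.2.2 and 9.1.2. State the maximum ethambutol exposure that the reconciled text permits, and whether days are counted cumulatively or continuously. Make the risk text in 5.2.2 and 9.1.2 match. Which passage changes is for the clinical team; no position is taken here on the right rule.

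Optionally, record visual symptoms as a specific item within the existing symptom and adverse-event review at visits during or after a replacement period. Those are weeks 16 and 24; weeks 4 and 8 fall before or at the start of the two-drug phase.

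The cost is protocol wording and, if the option is taken, one recorded item at visits already scheduled. No visit or test is added, and the sample size and analysis are unaffected.

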#### **5.5 Assessment of Drug Adherence:**

Participants should be asked to return the pill bottles and medication diary at each visit. Pill counts should be conducted at each visit and reconciled with quantities dispensed, and a review of medication diary to assess adherence to prescribed regimen and the onset of new symptoms should be conducted. If a participant misses a dose, they will receive guidance on making up missed dose

#### **5.6 Discontinuation of Study Drug Administration**

Treatment will continue for a maximum of 112 doses after study enrollment or 16 weeks post-randomization, whichever comes first. Treatment will be discontinued in the following circumstances:

1. Death
2. Primary care provider or participant request
3. ALT is noted to exceed ten times the upper limit of normal
4. A serious adverse event has occurred and is thought to be related to study drug and in the opinion of the investigator or attending physician warrants discontinuation of the study drug, or any intolerable or unacceptable adverse event (including clinically significant abnormal labs thought to be due to study drug) that in the opinion of the investigator or attending physician warrants discontinuation
5. Positive pregnancy test
6. Non-compliance with the regimen and timing that might result in dropping out from the study

7. Development of an intolerable AE due to study participation as determined by the Investigator, participant, or both.
8. Development of an intercurrent illness, condition, or procedural complication, which would interfere with the participant's continued participation.

Participants who have stopped taking study drugs may continue to participate in the study and will follow the appropriate procedures in the protocol.

Any participant who discontinues treatment for medical reasons, e.g. because of adverse events (AEs) or clinical laboratory abnormalities, should be followed up at medically appropriate intervals in order to evaluate the course and to ensure reversibility or stabilization of the abnormality or event. If a participant fails to return for a scheduled visit, a documented effort must be made to determine the reason. This information should be recorded in the study records.

